4.2 The Informed Consent Process

We will follow the DF/HCC Policy CON-100: Informed Consent Process to obtain and document informed consent. Study staff can review the study details, offer study participation, and obtain informed consent in-person or verbally. Both the written and the verbal consent forms describe all study procedures, information about potential risks and benefits of participation, and information regarding who they can contact for further questions. The forms also state that participation is voluntary, that participants can refuse to answer any questions, that they can withdraw from the study at any time, and that study participation is in no way related to their medical care. Study participants who do not provide consent will be asked the reason why they prefer to not participate in the study.

- **Verbal Consent Process:** We are requesting an alteration of HIPAA to allow for a waiver of Written Documentation of Consent. This study meets the requirements for a waiver as it is a Minimal Risk study, and all study procedures can be communicated verbally. This Waiver will allow study staff to recruit participants remotely to address barriers to study enrollment including infrequent in-person visits, lack of space in clinic, and patients’ time constraints. Verbal consent allows for greater flexibility while assuring patient safety in response to changing healthcare practices. Study staff will contact potential participants via telephone to guide them through verbal consent forms that describe all study procedures, information about potential risks and benefits of participation, and information regarding who they can contact for further questions. The participant will be given ample opportunity to ask questions and take their time to consider their participation. All patients who provide verbal consent will receive an unsigned copy of the written informed consent. The study staff may contact eligible patients to obtain verbal consent using the HIPAA-compliant verbal consent form. If the patient does not answer the phone study staff may leave a voicemail (Appendix 9.7, 9.8).
- **Spanish-speaking Consent Process:** Patients who speak Spanish will have all study procedures and information regarding risks, benefits and study contacts explained to them via the use of an interpreter (in-person or remotely) or a Spanish-speaking study staff member with a witness present. Study staff will sign the English verbal consent form and document interpreter information when necessary.
- For all patients who provide consent, we will obtain HIPAA authorization. This may be done remotely through the REDCap platform by the patient typing their name and checking an assurance confirming that the typed name acts as an electronic signature or in person.

4.3 Registration

Participants who meet eligibility criteria and provide informed consent will be registered in the Clinical Trials Management System (CTMS) OnCore, as required by per DF/HCC SOP REGIST-101. Registration will occur once the participant has completed the baseline assessment. Study staff will complete the protocol-specific eligibility checklist, verifying that the participant meets all inclusion and exclusion criteria.

4.4 Participant Communication Methods

It is important to access and maintain contact with participants through communication methods they are most comfortable with, including phone, text, and email correspondence. During the informed consent process, study staff will elicit patient preferences about methods of study contact to facilitate participation (e.g., scheduling study intervention sessions, sending reminders, etc.). The limitations of each method will be described to them in detail by the research coordinator. Specifically, patients may opt to pursue communication with study staff via phone, text, or email correspondence. Phone and email communication have been successful strategies to communicate with patients in prior psychosocial studies, and email and SMS text templates intended for study use can be found in Appendices 9.17, 9.18, 9.19, 9.20.

SMS Messaging. Participants may elect to provide a personal mobile phone number and provide permission to receive SMS messages via an online service (GoogleVoice) regarding the study that the study staff will monitor. Before doing so, participants will be informed of the limitations of using GoogleVoice, particularly emphasizing that it is not HIPAA-compliant and thus does not offer protection over their personal health information. Additionally, participants will be informed that this phone number is not monitored regularly and should not be used for urgent or emergency purposes. Participants will be advised that, in the case of an emergency, they should contact their care team or emergency services. In the event participants still prefer the use of text messaging, study staff will send brief messages containing limited information regarding intervention session reminders. Participants will be provided with the number for SMS study-related communications. Study staff will follow the templates as outlined in Appendix 9.19 and 9.21 for SMS communication. Under the discretion of trained study staff and extenuating circumstances, study staff may stray from the following templates to address scheduling/reminder situations not covered by the message templates. Under no circumstances will study staff ever screen or discuss personal medical history, exchange personal health information, or other sensitive information via SMS message. If a participant introduces sensitive information, including but not limited to the examples just listed, into a SMS message conversation, the study staff member will direct the participant to call them to discuss it further over the phone.

- Send Secure Email. Participants will be provided with the Partners Privacy language regarding encrypted emails and given the opportunity to opt-out of Send Secure emails. In previous psychosocial studies, participants have articulated difficulties with accessing encrypted emails and prefer the option to opt-out of such method of encrypted communication.

5.0 Study Design and Methods

5.1 Design/Study Type

The present protocol proposes to examine the single-arm pilot trial to examine feasibility and acceptability of a patient-centered, evidence-based, culturally competent, tailored intervention to encourage breast cancer survivors who have not begun taking adjuvant endocrine therapy to initiate the medication, enriching for Black, Hispanic/Latina, and Asian American BCS. AET initiation will be measured by a self-report questionnaire. Participants will complete assessments at baseline (within 14 days of consent), 1-month, and 3-months post-baseline measuring beliefs about AET necessity, satisfaction with patient-physician communication, perceived social support and quality of life.

5.2 Selection of Instruments

Instrument/Measure	Screening	Baseline (14-day window)	1-month follow-up (+/- 7 day)	3-month follow-up (+/- 7 day)
Chart Review	X			
Screening Questions (AET initiation)	X			
Demographics		X		
AET Initiation Question		X	X	X
Functional Assessment of Chronic Illness Therapy- Treatment Satisfaction-Patient Satisfaction (FACIT-TS-PS)		X	X	X
Beliefs about Medicines Questionnaire – Adjuvant Endocrine Therapy (BMQ-AET)		X	X	X
Multidimensional Scale of Perceived Social Support (MSPSS)		X	X	X
Functional Assessment of Cancer Therapy-Breast (FACT-B)		X	X	X
Hospital Anxiety and Depression Scale (HADS)		X	X	X
Self-Efficacy for Managing Symptoms Questionnaire (Self-Efficacy for Symptoms)		X	X	X
Measure of Current Status – Part A (MOCS)		X	X	X
Client Satisfaction Questionnaire (CSQ)			X	

Screening:

EHR Factors: The following information will be collected from participant EHR: MGH Main vs Affiliate site vs DFCI sites, demographic information, breast cancer stage, treatment (e.g., surgery, chemotherapy, radiation), AET type, approximate recommended AET start date, and medical or psychological co-morbidities.

AET Initiation questions: A question will be administered asking patients whether they have started taking their daily AET (yes vs. no). Patients who have not yet started AET will be considered eligible for study participation. Patients will also be asked how hesitant they are about starting their recommended hormonal therapy medication on a scale of 0-10.

Outcome Measures:

Demographics Questionnaire: Participants will self-report their age, gender, race/ethnicity, marital status, education level, and relationship status.

AET Initiation Question: This one item instrument will ask patients: At different times throughout your participation in this study, you may or may not be taking/have started taking your hormonal therapy. “At this time, are you currently taking your hormonal therapy (e.g., Tamoxifen, Anastrozole/Arimidex, Exemestane/Aromasin, Letrozole/Femara)?” Patients will self-report their initiation of endocrine therapy.

Functional Assessment of Chronic Illness Therapy-Treatment Satisfaction-Patient Satisfaction (FACIT-TS-PS):³³ This thirty-item questionnaire will be administered to patients to assess satisfaction with communication with clinicians and nurses and consists of items such as “Did your doctor show genuine concern for you?”. Each item is measured on a Likert-type scale of 0 (No, not at all) to 3 (Yes, and as much as I wanted). Subscale scores are computed by summing each individual item, multiplying the sum by the number of items in the subscale and dividing by the number of items answered. Over 50% of items in a subscale must be completed to receive a valid score. Subscales include physician communication (0-36 score range), treatment staff communication (0-12), technical competence (0-9), nurse communication (0-9), and confidence and trust (0-12).

Beliefs about Medicines Questionnaire – Adjuvant Endocrine Therapy (BMQ-AET):³⁴ This 10-item questionnaire will be administered to assess the perceived need for AET versus concerns about side effects or other negative consequences (i.e., Necessity-Concerns framework). The BMQ-AET has been used in studies measuring endocrine therapy adherence. This study will use one of the two scales, which is computed measuring perceived need for medication and concerns about disruptive medication effects. Items are measured on a Likert-type scale of 1 (strongly agree) to 5 (strongly disagree). Total scores are calculated by finding the sum of subscales that range 10-50.

Multidimensional Scale of Perceived Social Support (MSPSS):^{35,36} This 12-item questionnaire will be administered to patients to assess patients’ perceived social support. The validated and reliable scale consists of items, such as “my family really tries to help me,” and is measured on a 7-point Likert scale. The item is divided into 3 subscales: family, friends, and significant other and the range of the total scale is 1-7.

Functional Assessment of Cancer Therapy-Breast (FACT-B):³⁷ The FACT-B is a validated measure used to assess multidimensional quality of life in patients with breast cancer. The measure captures five domains: physical well-being, social/family well-being, emotional well-being, functional well-being, and additional concerns. Each item is answered on a Likert-type scale of 0 (not at all) to 5 (very much). Subscale scores are computed by summing each individual item, multiplying the sum by the number of items in the subscale and dividing by the number of items answered. Total FACT-B scores can range from 0-148.

Hospital Anxiety and Depression Scale (HADS):^{38,39} The HADS is a valid self-report measure for assessing anxiety and depressive symptoms among patients in non-psychiatric hospitals. The 14-item measure contains seven questions to assess depressive symptoms and seven questions to assess anxiety symptoms to distinguish between the two. Patients indicate how they have been feeling on average over the past week. Each item is answered on a scale of 1 to 4. The four possible answer choices vary and adjust for each question. Total subscale scores range from 0-21.

Self-Efficacy for Managing Symptoms Questionnaire (Self-Efficacy for Symptoms):⁴⁰ The Self-Efficacy for Symptoms Questionnaire is a modified version of the self-efficacy scale to assess patient self-efficacy in managing symptoms related to their endocrine therapy medication. The measure asks patients to rate their confidence on a scale of 1 (not at all confident) to 10 (very confident) in their ability to decrease or control the side effects of their medication. This is an 8-item scale, and total scores range from 1-10.

Measure of Current Status (MOCS):⁴¹ The MOCS is a 13-item scale which measures patients' current self-perceived ability on several skills. Examples of targeted content areas are ability to relax, restructure maladaptive thoughts, and choose appropriate coping responses. Each of the 13 items is answered on a scale of 0 (I cannot do this at all) to 4 (I can do this extremely well).

Other demographic and treatment-related factors affecting initiation will be collected from the EHR and examined as covariates.

Intervention Acceptability:

Client Satisfaction Questionnaire (CSQ):⁴² The CSQ is a 3-item, validated measure to assess satisfaction with services provided to the patient, and asks questions such as, "to what extent has our program met your needs?" Each item is answered on a scale of 1-4. This will be administered at the 1-month assessment to evaluate intervention participants only to examine intervention acceptability. The total score range is 3-12.

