3.0 Research Subject Selection

3.1 Partial waiver of HIPAA Authorization

We request a partial waiver of HIPAA Authorization in order for our team to perform an initial screening process that requires review of the electronic medical record. This partial waiver is being requested to allow the research team to screen the oncology clinic schedules and identify potential study participants from a minimal chart review. In accordance with the DF/HCC policy: (1) this Waiver is being sought solely to review Protected Health Information as necessary to prepare a research protocol; (2) the Waiver will not include removing Protected Health Information from the Covered Entity by the researcher, and (3) the Protected Health Information for which we are requesting access is necessary for research purposes.

For individuals who provide verbal consent to participate in the study, we will obtain HIPAA authorization, as described in section 4.2 (Informed Consent Process).

Table 1. Inclusion Criteria
1. Female
2. Age 21 or older

3. Diagnosis of early-stage (Stage I-IIIB), hormone receptor-positive breast cancer
4. Recommended to start AET at least 3 weeks prior and not currently taking AET OR recommended to start AET in the future and reports hesitations to start AET as determined by a score of ≥ 4 (range =0-10) when asked "How hesitant are you about starting your recommended hormonal therapy? (0=Not at all hesitant and 10 = Extremely hesitant)"
5. Ability to read and respond in English or Spanish
6. Eastern Cooperative Oncology Group (ECOG) performance status ≤ 2
7. For at least 10 participants, identify as a member of a racial or ethnic minority community per self-report
Exclusion criteria
1. Uncontrolled psychosis, active suicidal ideation, psychiatric hospitalization within the past year
2. Cognitive impairment that prohibits participation in the study
3. Undergoing primary treatment for other cancer (i.e., advanced stage cancer)
4. Participating in a clinical trial involving AET
5. Diagnosis of Stage 0 (DCIS) breast cancer

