7.5 Analysis Plan

Aim 1: Feasibility and acceptability will be measured by rates of enrollment (>50%), participant retention (>70%), intervention attendance (>70% attending at least 1 of 2 sessions), and intervention satisfaction (>75% reporting average satisfaction greater than the CSQ's midpoint).

Aim 2: First, data will be analyzed with the intention-to-treat principle and assessed for statistical assumptions and patterns of missingness, implementing Multiple Imputation with maximum likelihood if appropriate. Sample size justification. We may over-accrue to ensure that a total of up to 45 BCS complete the study. This pilot study will provide a preliminary estimate of the rate of AET initiation within one month from baseline. With up to 30 participants, the width of the exact 95% confidence interval (CI) for the rate of AET initiation at one month will be at most 37.4% (i.e., +/- 18.7%). If at least 24% of participants initiate AET within one month, the study will rule out a post-intervention initiation rate of lower than 10% based on the lower limit of the exact 95% CI. We will conduct exploratory analyses to examine whether participants' baseline characteristics are associated with AET initiation at one month using Fisher's exact tests and unpaired t-tests. For secondary outcomes, we will conduct paired samples t-tests to assess intervention-related changes in satisfaction with communication with clinicians and treatment, Necessity-Concerns Framework, perceived support, self-efficacy for managing side effects, and QOL from baseline to one-month post-baseline. In addition, we will use linear mixed effects regression models to evaluate the change in secondary outcomes across all three assessment time points. We will interpret 95% Confidence Intervals and Cohen's d effect sizes ($D = [(Mean 1) - (Mean 2)] / \text{pooled Standard Deviation}$), with magnitudes of 0.3, 0.5, and 0.8 for small, medium, and large effects, respectively. We will conduct sensitivity analyses to examine whether changes in outcomes are differ among racial and ethnic groups.

Participants will be given the opportunity to receive a summary of study results at the completion of the study. If a request is made, the study staff will provide the participant with an abstract of the study at the end of data collection and analysis.

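### The only follow-up item on AET initiation asks about current use, so a woman who starts and stops before the survey is recorded as a non-initiator

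*Combined protocol and SAP*

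**What the plan says.** Section 5.1 states that "AET initiation will be measured by a self-report questionnaire". Section 5.2 describes that measure: "This one item instrument will ask patients" a question at baseline, 1 month and 3 months. The preamble tells the woman that "you may or may not be taking/have started taking your hormonal therapy", but the question then put to her is "At this time, are you currently taking your hormonal therapy", with drug names as examples. Section 5.2 labels the answer as initiation: "Patients will self-report their initiation of endocrine therapy".

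Section 7.5 sets the Aim 2 target: "This pilot study will provide a preliminary estimate of the rate of AET initiation within one month from baseline". The sentence about ruling out 10% also speaks of initiating within one month. The confidence interval sentence and the comparison of baseline characteristics speak of initiation at one month. The Aim 2 hypothesis in section 2.0 is that women will be more likely to have started.

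At entry, one route in Table 1 reads "Recommended to start AET at least 3 weeks prior and not currently taking AET". The screening question in section 5.2 and the phone script in Appendix 9.5 ask instead whether she has started.

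**The concern.** Starting within an interval is a cumulative event: once it has happened, it stays true. Taking the drug at the time of a survey is a status that can reverse. The plan names the former (in two of its four phrasings) and measures the latter. The two differ for a woman who starts after baseline and stops before she is surveyed.

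This matters because sections 1.2 and 1.3 set initiation apart from adherence, and section 1.3 says that this study aims at initiation. Sections 1.4 and 7.2 say that the pilot data will support an application for a full-scale efficacy trial. If the rate carried forward is current use under the name of initiation, the later trial may be planned on the wrong quantity. A first dose that was never asked about is also hard to recover afterwards.

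**Working it through.** **1. Could another source recover her?** The instrument has one item. The schedule in section 5.2 places chart review at screening only. The listed record fields include AET type and the approximate recommended start date, but no actual start or stop date. Other record data in section 5.2 are for use as covariates. Section 7.5 gives no coding rule for a woman who started and stopped. Her no is therefore the only information about her, and she counts as a non-initiator.

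**2. Reproduce the plan's figures.** Inputs from section 7.5: n=30, exact 95% interval, maximum width 37.4%, and an observed rate of at least 24% ruling out a rate below 10%. The Clopper-Pearson limits for x of n are

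- lower = Beta quantile(0.025; x, n−x+1)
- upper = Beta quantile(0.975; x+1, n−x)

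At n=30 the widest interval is at x=15, with width 37.41%, which matches. For the threshold, 0.24 × 30 = 7.2, so the smallest qualifying whole count is 8.

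| Count | Rate | Exact 95% lower limit |
|---|---|---|
| 8/30 | 26.7% | 12.3% |
| 7/30 | 23.3% | 9.9% |
| 8/35 | 22.9% | 10.4% |
| 7/35 | 20.0% | 8.4% |

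Both of the plan's statements reproduce. The n=35 rows use the accrual figure in section 7.2.

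**3. Effect of the item.** If x women truly initiated and s of them stopped before the survey, the observed count is x − s. Each stop costs 1/30 = 3.3 points (1/35 = 2.9 points at n=35). The lower limit falls below 10% when x − s ≤ 7. With 8 true initiators, one stop is enough. With 9 it takes two, and with 10 it takes three.

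**4. Range for the unknown stopping share.** Let p be true initiation and q the share of initiators who have stopped by the survey. The documents give no q, so 0 to 30% is an assumption. The expected observed rate is p(1−q), and the chance of at least 8 of 30 is a binomial tail at that rate.

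| q | p=30%: expected rate | P(≥8/30) | p=40%: expected rate | P(≥8/30) |
|---|---|---|---|---|
| 0 | 30.0% | 0.719 | 40% | 0.956 |
| 5% | 28.5% | 0.655 | 38% | 0.932 |
| 10% | 27.0% | 0.585 | 36% | 0.898 |
| 20% | 24.0% | 0.435 | 32% | 0.792 |
| 30% | 21.0% | 0.285 | 28% | 0.632 |

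**The case against.** The strongest reply is that the endpoint is not settled as an interval event. Section 7.5 says *at one month* as often as *within one month*, and current use fits the former. Current use is also a defensible and stricter outcome: counting any dose as success credits a woman who took one tablet. This stands in part. The item does not contradict one clear definition, because the plan mixes two. But the ambiguity has to be resolved, and under the *within* reading the item cannot supply the answer.

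The size may also be small. Section 5.3 puts the sessions about two weeks apart and aims to hold both before the planned start date. If session 1 falls on the baseline day, a woman who starts after session 2 starts on day 14 or later. With a 30-day month the survey falls on days 23 to 37, so she has about 9 to 23 days in which to stop. This is fair, although the timing is an aim and not a requirement. Section 1.2 calls adverse effects common with AET, which says nothing about stopping within weeks.

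Four stronger readings are tempting, and the documents do not support them:

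- **A decision rule that turns on one woman.** The 24% and 10% figures illustrate precision under the sample size justification, and no go or no-go depends on them. One participant always separates the last passing count from the first failing one, and here that requires exactly 8 true initiators.
- **Damage to a 3-month result.** A no at 3 months cannot separate never started from started and stopped, but section 7.5 specifies an initiation estimate only at one month.
- **Past users counted as new initiators.** Table 1 read alone would admit a woman who had started and stopped. The screening question and the phone script turn her away, so the case does not arise if screening is followed. What remains is a wording conflict.
- **Harm to the primary endpoint.** Section 7.1 bases it on enrollment, retention, attendance and satisfaction. None of these uses the AET item.

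**Conclusion.** The mismatch between item and estimate holds. Read as initiation within one month, the Aim 2 rate is biased downward by women who start and stop before the survey: 3.3 points for each such woman at n=30. The total is unknown because no early-stopping rate is given, and it may be small. The drop in the lower limit from 12.3% to 9.9% is an edge case, not an expected result. The conclusion assumes truthful answers and no follow-up source beyond those described. It concerns a secondary pilot outcome. It is worth correcting because the estimate is meant to inform a larger trial and the change is cheap.

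**What to change.** - At 1 and 3 months, add one item asking whether any hormonal therapy has been taken since baseline (yes or no, with the date of first dose). Keep the current-use item.
- In section 7.5, define initiation within one month from the new item and its date. Report current use at the visit as a separate, named outcome, and use one phrase for each throughout. The date also allows the one-month limit to be applied to surveys returned anywhere in the ±7-day window.
- Reconcile Table 1 (not currently taking) with the screening question and the phone scripts (have started), so that a woman who started and stopped before screening is handled the same way in each.

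The cost is one question at two existing assessments, a short definition and an eligibility edit, with some recall error in the first-dose date. Planned precision is unchanged (maximum width 37.4% at n=30). Redefining the endpoint as current use at one month would also remove the mismatch with no new item, but the study would then not estimate initiation.

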1.4 Innovation of Proposed Study

This research project aims to reduce risk of recurrence and prevent second primary breast cancer by increasing initiation of AET for BCS who have failed or delayed AET initiation or are hesitant to start, with particular

attention to Black, Hispanic/Latina and Asian American BCS. The data from this Phase 2 single-arm pilot trial to test a behavioral intervention developed using feedback from Phase 1 (21-331) to improve initiation, will be used to apply for an NIH grant to conduct a full-scale efficacy trial of the intervention. This is an area of important clinical investigation that does not necessitate a new treatment or technology, but rather points to the critical need to improve how and whether patients engage with an efficacious, life-saving therapy. In the short-term, this study has the potential to improve understanding of AET need and efficacy and increase initiation by mitigating barriers and enhancing self-efficacy. To minimize burden and increase access, we propose to deliver the intervention via ZOOM™, a HIPAA-secure Massachusetts General Hospital (MGH)-approved software. The study staff may also administer these sessions in person or via phone if necessary. This intervention has minimal risk and is likely to improve patient satisfaction with communication with clinicians and management of AET-related side effects. In the long-term, this study may improve patient outcomes by preventing second primary tumors, recurrence, and disease-related mortality while promoting the quality of life of BCS and reducing the racial and ethnic disparity in breast cancer outcomes.

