The intervention and study materials will be translated into Spanish and delivered by nurse practitioner, [name], in either English or Spanish. An interpreter will be present either in person or remotely for the intervention for patients who speak Spanish only. Both sessions will take place within one month of the baseline assessment. The intervention will target known modifiable barriers to AET initiation, including support and communication with clinicians, perceived therapeutic efficacy of AET, and managing expectations of symptoms and side effects, but will be primarily driven by barriers identified by the patient. Therefore, the session will begin by probing and identifying the individual and culture-specific barriers to initiation in multiple domains. The interventionist and patient will then problem-solve barriers to initiation through motivational interviewing, cognitive-behavioral techniques, and medication education. The intervention is informed by the Health Belief Model (HBM), the Cognitive Model of Adjustment to Cancer, and Motivational Interviewing Techniques. First, the intervention will address perceived risk and medication efficacy in line with the HBM, which maintains that the health behavior (i.e., initiating AET) will be adopted if the patient perceives (a) risk for a condition, (b) that the medication will reduce risk, (c) that benefits outweigh costs, and (d) self-efficacy for taking medication. Second, driven by the Cognitive Model of Adjustment to Cancer, the intervention will include strategies for enhancing coping with side effects, reframing cognitive self-talk about AET efficacy, and identifying and enhancing social support. CBT is effective in helping patients manage concerns, fears, and actual cancer-related side effects. Finally, Motivational Interviewing techniques will help the patient explore and resolve ambivalence with attention to their readiness for change. Sessions will be audio-recorded and at least 10% will be reviewed for treatment fidelity. Intervention acceptability will be evaluated using the CSQ.

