7.2 Sample Size

To determine feasibility in a single-arm pilot trial (up to N=35), estimate effect size, and finalize the intervention and study protocol to apply for an NIH grant to conduct a full-scale efficacy trial.

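### The BMQ-AET total adds need and concern items under one coding with no stated reversal or direction, and section 7.5 names no score, so the sign of a change in beliefs cannot be interpreted

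*Combined protocol and SAP*

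**What the plan says.** In the combined protocol and SAP, section 5.2 (Selection of Instruments) introduces the BMQ-AET as a ten-item questionnaire given to "assess the perceived need for AET versus concerns about side effects or other negative consequences (i.e., Necessity-Concerns framework"). One response coding is given for all items: "Items are measured on a Likert-type scale of 1 (strongly agree) to 5 (strongly disagree"). The scoring rule is "Total scores are calculated by finding the sum of subscales that range 10-50". The same paragraph also says "This study will use one of the two scales, which is computed measuring perceived need for medication and concerns about disruptive medication effects". It mentions no reversed items and does not say whether a high or a low score is favourable.

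Section 7.5 (Analysis Plan) plans paired t-tests from baseline to one month on "satisfaction with communication with clinicians and treatment, Necessity-Concerns Framework, perceived support, self-efficacy for managing side effects, and QOL", then mixed models over the three assessments and Cohen's d. For beliefs it names the framework only, not a total, a subscale or a difference.

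Other sections describe this outcome differently. Sections 1.1, 1.2 and 5.1 refer only to beliefs about necessity. The lists of changes to be explored in sections 2.0 and 7.1 leave medication beliefs out.

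**The concern.** Need and concerns are opposed constructs, and the intervention is meant to act on both. Section 1.4 expects that "this study has the potential to improve understanding of AET need and efficacy". Section 5.3 lists among the targeted barriers "perceived therapeutic efficacy of AET, and managing expectations of symptoms and side effects", and presents cognitive-behavioural techniques as a means of managing concerns and fears. Section 1.2 treats doubts about efficacy and fear of toxicity as separate modifiable factors.

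With 1 for strong agreement on every item, a woman who becomes more convinced of need scores lower on the need items. A woman who becomes less worried scores higher on the concern items. Adding the two sets puts the two benefits in opposite directions.

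At stake is whether the mean change and Cohen's d for this outcome can be read at all. That matters because section 7.2 gives among the pilot's purposes "To determine feasibility in a single-arm pilot trial (up to N=35), estimate effect size, and finalize the intervention and study protocol".

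**Working it through.** **Step 1. Reproduce the stated range.** Inputs from section 5.2: ten items, each coded 1 to 5. Minimum 10 × 1 = 10 and maximum 10 × 5 = 50, which agrees with the plan. The total must therefore contain all ten items. A subscale of nine items or fewer reaches at most 9 × 5 = 45, and a need-minus-concerns difference with five items each would run from 5 - 25 = -20 to 25 - 5 = +20.

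**Step 2. Does the range show whether concern items are reversed?** Reversal replaces a concern item x by 6 - x, which again runs from 1 to 5. The reversed total is also 10 to 50, so the range does not distinguish the two rules.

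**Step 3. Direction of the total as written.** Let k be the number of need items and m the number of concern items, with k + m = 10. The documents do not give the split, so three are shown. If every item moves one point in the intended direction, need contributes -k, concerns contribute +m, and both together give m - k. The most favourable profile (maximum need, no concerns) scores k + 5m and its exact opposite scores 5k + m.

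| Need/concern items (assumed) | Need only | Concerns only | Both | Most favourable profile | Exact opposite |
|---|---|---|---|---|---|
| 5/5 | -5 | +5 | 0 | 30 | 30 |
| 4/6 | -4 | +6 | +2 | 34 | 26 |
| 6/4 | -6 | +4 | -2 | 26 | 34 |

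The total spans 50 - 10 = 40 points. With a 5/5 split, a change of +5 arises equally from concerns easing by one point per item (intended) and from perceived need weakening by one point per item (not intended). With concern items reversed, the joint intended change is -k - m = -10 for every split, so lower is favourable.

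**Step 4. Unequal shifts (assumed 5/5 split).** Need 0.5 and concerns 0.3 points per item: -2.5 + 1.5 = -1.0. Need 0.3 and concerns 0.5: -1.5 + 2.5 = +1.0. Two beneficial patterns give opposite signs. With reversal both give -4.0.

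**Step 5. What this could do to the paired t-test.** Assumptions: n = 30 (the figure used in section 7.5), two-sided 5% level (none is stated for these tests), a standardised change of 0.5 on each subscale (mean change divided by SD of change), and equal SDs. Power comes from the noncentral t with noncentrality d × √n.
- One subscale alone: 0.5 × √30 = 2.74, power 0.75.
- Unreversed sum: the mean changes cancel, so d = 0 and the rejection probability is 0.05.
- Reversed sum: d = 1/√(2 - 2r), where r is the correlation of the raw changes. For r from -0.5 to 0.3, d is 0.58 to 0.85 and power 0.86 to 0.99.

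**Step 6. Two other scoring texts in section 5.2.**
- HADS: seven items at 1 to 4 give 7 × 1 = 7 to 7 × 4 = 28, whereas the stated subscale range is 0 to 21, which seven four-choice items reach at 0 to 3. The 1-to-4 wording may only number the answer choices. For the CSQ, however, nearly the same wording is the scoring code (three items, 3 × 1 = 3 to 3 × 4 = 12, as stated).
- FACT-B: with items at 0 to 5, 148/5 = 29.6; 29 items give at most 145 and 30 give 150. No whole number of items gives the stated maximum of 148.

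**The case against.** The strongest reply is that the protocol is silent on reversal, and silence does not show that the items will be summed raw. No instrument in section 5.2 has its reversals written out, the paragraph cites a psychometric paper that may contain the scoring, and the wording frames need against concerns as a contrast. The sentence about using one scale of two can also be read as one scale covering both constructs, which would fit ten items and 10 to 50. This stands in part. A reader might infer that the trial is committed to a score that cancels its own effect and that the belief result will be null. The documents do not support that: the offset occurs only if concern items are left unreversed, and it is complete only if the summed shifts are equal.

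The reply does not settle the matter, though. Section 5.2 states a rule, and following it literally produces the offset. If reversal is intended, it still has to be written, and so does the less obvious fact that low scores would then be favourable. The quotations on intended direction are indirect, since neither says that BMQ concern scores should fall, but the account of the intervention in section 5.3 as a whole supports that reading.

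A reader might also infer that the depression follow-up trigger in section 5.6 is set on the wrong scale. That goes too far. The stated 0-to-21 range favours reading the trigger on that range, and what remains is an inconsistency in the item wording. Nor is the HADS among the secondary outcomes listed in section 7.5.

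**Conclusion.** The concern holds in a conditional form. As written, the BMQ-AET total cannot show from its sign whether beliefs improved, and section 7.5 does not repair this because it names no score. Under the literal rule, a one-point intended shift on every item nets 0, +2 or -2 on a 40-point range. If only one construct moves, the full 4 to 6 points remain, but the sign depends on which one it was. The item splits, shift sizes, SDs and correlations are assumptions; the single coding, the ten-item sum and the absence of any stated reversal or direction are in the text.

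The reach is limited to one secondary outcome of a single-arm pilot: its paired t-test, mixed model and Cohen's d. The feasibility and acceptability endpoints and the initiation rate are untouched. No data are lost, since the items can be rescored before analysis. The HADS text is an inconsistency to reconcile, and the FACT-B item range is a clerical slip for which no analytic effect is claimed.

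**What to change.** - **Section 5.2, BMQ-AET:** replace the summed total with separate Necessity and Concerns scores, listing the items in each and stating which direction is favourable. At minimum, if one total is kept, state that concern items are reversed and that lower totals are then favourable under the present coding. Rewrite the sentence about using one of two scales to agree with whichever is chosen.
- **Section 7.5:** name the score or scores that enter the paired t-tests, mixed models and Cohen's d. A Necessity-minus-Concerns difference is optional.
- **Section 5.2, HADS, and section 5.6:** reconcile the item coding with the stated subscale range, so that the follow-up trigger refers to one coding. No threshold is proposed here.
- **Section 5.2, FACT-B:** correct the item range so that it agrees with the stated total.

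The cost is an edit to the scoring text and the data dictionary; the same items are collected at the same visits. The downside of separate scores is two belief results in place of one, each describing only its own construct.
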